7.5 Analysis of Safety

Some analyses that do not depend on the measurement time point such as the summary of TEAEs will be performed for not only Phase 1 part and Phase 2 part separately but also Phase 1/Phase 2 part totally. The details are described in the following Sections.

7.5.1 DLT (Phase 1 part only)

Analysis set: DDAS

The following data will be summarized for the DDAS.

- For DLT incidence, the number and percentage of subjects will be summarized.
- The posterior mean of the DLT rate will be estimated from the Bayesian-CRM using the following statistical models.

The dose-response relationship against DLT occurrence assumes power model, as shown below.

The occurrence of DLTs for each patient should follow the Bernoulli distribution.

Power model:

$$\Pr(Y_{ik} = 1 | \text{dose} = d_k) = \pi(x_k, \alpha) = x_k^{\exp(\alpha)}$$

where α is the model parameter, x_k is the skeleton of DLT incidence probability in the dose for number k used in the statistical model, d_k is the administered dose level of number k , Y_{ik} is the presence/absence of DLT in subject i and dose level of number k (1 is present) and $\pi(\bullet)$ is the probability of DLT occurrence under given conditions.

Prior distribution of parameters assumed a normal distribution with the mean as 0 and variance as 1.26. Using the ESS, the variance of the prior distribution of a parameter α was set so that the information content of prior distribution in the power model is approximately 1 subject.

The skeletons to be used in the statistical model are $x_1 = 0.08$ and $x_2 = 0.17$.

7.5.2 Adverse Events (AEs)

[Phase 1 part, Phase 2 part, Phase 1/Phase 2 part]

Analysis set: SAF

AEs will be coded using MedDRA and graded using NCI-CTCAE (V4.0). All AE recorded on treatment including within 30 days after the last administration will be summarized.

TEAEs will be graded using National Cancer Institute's Common Terminology Criteria for AEs (NCI-CTCAE).

An overview table will include the following details:

- Number and percentage of subjects with TEAEs
- Number and percentage of subjects with ASP2215-related TEAEs
- Number and percentage of subjects with regimen-related TEAEs
- Number and percentage of subjects with serious TEAEs
- Number and percentage of subjects with ASP2215-related serious TEAEs
- Number and percentage of subjects with regimen-related serious TEAEs
- Number and percentage of subjects with TEAEs leading to dose reduction of ASP2215
- Number and percentage of subjects with ASP2215-related TEAEs leading to dose reduction of ASP2215

- Number and percentage of subjects with regimen-related TEAEs leading to dose reduction of ASP2215
- Number and percentage of subjects with TEAEs leading to dose interruption of ASP2215
- Number and percentage of subjects with ASP2215-related TEAEs leading to dose interruption of ASP2215
- Number and percentage of subjects with regimen-related TEAEs leading to dose interruption of ASP2215
- Number and percentage of subjects with TEAEs leading to withdrawal of treatment
- Number and percentage of subjects with ASP2215-related TEAEs leading to withdrawal of treatment
- Number and percentage of subjects with regimen-related TEAEs leading to withdrawal of treatment
- Number and percentage of subjects with TEAEs leading to death
- Number and percentage of subjects with ASP2215-related TEAEs leading to death
- Number and percentage of subjects with regimen-related TEAEs leading to death
- Number and percentage of subjects with grade 3 or higher TEAEs
- Number and percentage of subjects with ASP2215-related grade 3 or higher TEAEs
- Number and percentage of subjects with regimen-related grade 3 or higher TEAEs
- Number and percentage of subjects with deaths
- Number of TEAEs
- Number of ASP2215-related TEAEs
- Number of regimen-related TEAEs
- Number of serious TEAEs
- Number of ASP2215-related serious TEAEs
- Number of regimen-related serious TEAEs
- Number of TEAEs leading to dose reduction of ASP2215
- Number of ASP2215-related TEAEs leading to dose reduction of ASP2215
- Number of regimen-related TEAEs leading to dose reduction of ASP2215
- Number of TEAEs leading to dose interruption of ASP2215
- Number of ASP2215-related TEAEs leading to dose interruption of ASP2215
- Number of regimen-related TEAEs leading to dose interruption of ASP2215
- Number of TEAEs leading to withdrawal of treatment
- Number of ASP2215-related TEAEs leading to withdrawal of treatment
- Number of regimen-related TEAEs leading to withdrawal of treatment
- Number of TEAEs leading to death
- Number of ASP2215-related TEAEs leading to death
- Number of regimen-related TEAEs leading to death
- Number of grade 3 or higher TEAEs
- Number of ASP2215-related grade 3 or higher TEAEs
- Number of regimen-related grade 3 or higher TEAEs

The number and percentage of subjects with TEAEs, as classified by SOC and PT will be summarized. Summaries will be provided for:

- TEAEs
- ASP2215-related TEAEs
- Regimen-related TEAEs
- Serious TEAEs
- ASP2215-related serious TEAEs
- Regimen-related serious TEAEs
- TEAEs leading to dose reduction of ASP2215
- ASP2215-related TEAEs leading to dose reduction of ASP2215
- Regimen-related TEAEs leading to dose reduction of ASP2215
- TEAEs leading to dose interruption of ASP2215
- ASP2215-related TEAEs leading to dose interruption of ASP2215
- Regimen-related TEAEs leading to dose interruption of ASP2215
- TEAEs leading to withdrawal of treatment
- ASP2215-related TEAEs leading to withdrawal of treatment
- Regimen-related TEAEs leading to withdrawal of treatment
- TEAEs leading to death
- ASP2215-related TEAEs leading to death
- Regimen-related TEAEs leading to death
- Grade 3 or higher TEAEs
- ASP2215-related grade 3 or higher TEAEs
- Regimen-related grade 3 or higher TEAEs
- Common ($\geq 10\%$) TEAEs excluding serious adverse events

AE summary tables will include subject counts as opposed to AE counts. If a subject experiences more than one episode of a particular AE, that subject will be counted only once for that event. If a subject has more than one AE that code to the same preferred term, the subject will be counted only once for that preferred term. Similarly, if a subject has more than one AE within a body system, the subject will be counted only once in that body system.

The number and percentage of subjects with TEAEs, as classified by SOC and PT will also be summarized by NCI-CTCAE severity grade and by relationship to ASP2215 and regimen. In the subject count, if a subject has multiple TEAEs with the same SOC or PT, but with differing severity grade or relationship, then the subject will be counted only once with the worst severity grade and highest degree of relationship, however, if any of the severity grade or relationship values are missing then the subject will be counted only once with missing severity grade or relationship.

AESI are defined in the Safety Review Plan for ASP2215 as specified in (Appendix 2).

The number and percentage of subjects with TEAE of special safety interest, as classified by AESI category and PT will be summarized for the followings:

- TEAEs with special safety interest
- Grade 3 or higher TEAEs with special safety interest

- ASP2215-related Grade 3 or higher TEAEs with special safety interest
- Regimen-related Grade 3 or higher TEAEs with special safety interest

All AEs, deaths, SAEs and withdrawals due to AEs will be displayed in listings.

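### In the TEAE table by CTCAE grade, a single ungraded event hides a subject's known Grade 3–5 event, so the table can disagree with the Grade 3 or higher table

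*SAP*

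**What the plan says.** SAP Section 7.5.2 plans a table of TEAEs by SOC and PT, broken down by CTCAE grade and by relationship. Where a subject has several events in one SOC or PT, the default is that "the subject will be counted only once with the worst severity grade and highest degree of relationship". The same sentence then makes an exception: "if any of the severity grade or relationship values are missing then the subject will be counted only once with missing severity grade", or with missing relationship.

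The section also plans two other counts that depend on grade. The overview table has a line for "Number and percentage of subjects with grade 3 or higher TEAEs", and a separate SOC and PT table covers Grade 3 or higher TEAEs. The counting unit is the same throughout: "AE summary tables will include subject counts as opposed to AE counts", with each subject counted once per PT and once per SOC. No missing-grade exception is stated for these two counts.

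Nothing elsewhere fills in a missing grade. For adverse events, Section 7.11.1 imputes only start and stop dates. Section 6.2 deals with missing causality, which it treats as related, but has no matching rule for grade.

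**The concern.** A by-grade table is there to show the worst severity each subject reached. An ungraded event cannot lower a grade that is already known, yet the exception is triggered by any missing value rather than by all values being missing. A subject with a documented Grade 4 or Grade 5 event then drops out of the Grade 4 or Grade 5 column.

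Two things are at stake. The by-grade table can understate the number of subjects with Grade 3–5 events. It can also fail to reconcile, row by row, with the Grade 3 or higher table in the same section, although both count subjects in the SAF under the same once-per-SOC and once-per-PT rule.

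The point concerns severity only. For relationship the exception is consistent with Section 6.2: missing causality is treated as related, so the possible, probable and missing categories together still give the related count.

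**Working it through.** The SAP states no figure that depends on this rule, so there is none to reproduce. The check has two parts.

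**1. The rules applied to example subjects.** Each line is one subject's set of grades within one SOC or PT.

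| Grades in the row | By-grade table, SAP rule | In Grade 3 or higher table? | By-grade table, worst non-missing grade |
|---|---|---|---|
| 4 | 4 | yes | 4 |
| 3, 2 | 3 | yes | 3 |
| 4, missing | missing | yes | 4 |
| 5, 1, missing | missing | yes | 5 |
| 1, missing | missing | no | 1 |
| missing | missing | no | missing |

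With no missing grade, the tables agree. In the third and fourth lines they do not: the subject is in the Grade 3 or higher table but in none of the Grade 3–5 columns. With the worst non-missing grade, the Grade 3, 4 and 5 columns sum to the Grade 3 or higher count in every case.

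**2. How often this could happen.** The inputs are assumptions, because the SAP gives neither of them:
- q, the probability that an event has no grade, independently across events: 0.5%, 1% and 2%;
- m, the number of TEAEs the subject has in the row, one of them a known Grade 3–5 event: 2, 4 and 8. The smaller values are meant to represent a PT row and the largest a busy SOC row.

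The known event is hidden if at least one of the other m − 1 events is ungraded:

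P(hidden) = 1 − (1 − q)^(m − 1)

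For example, with q = 1% and m = 8: 1 − 0.99^7 = 0.0679.

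| | q = 0.5% | q = 1% | q = 2% |
|---|---|---|---|
| m = 2 | 0.5% | 1.0% | 2.0% |
| m = 4 | 1.5% | 3.0% | 5.9% |
| m = 8 | 3.4% | 6.8% | 13.2% |

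With q = 0 the probability is 0 for every m. The effect grows with m, so SOC rows are hit harder than PT rows.

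In subjects: Section 4.1.1 plans approximately 80 in Phase 2, so each displaced subject moves a row by 1/80 = 1.25 percentage points. With q = 1% and m = 2, the expected number displaced in a PT row is at most 80 × 0.01 = 0.8, and that only if all 80 had a Grade 3–5 event in it.

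**The case against.** The strongest reply is that the rule is explicit, prespecified and honest about uncertainty. An ungraded event might be worse than the known one: with Grade 4 and missing, the true worst grade could be 5; with Grade 1 and missing, it could be anything up to 5. On this view the worst grade really is unknown, the Grade 3 or higher table measures something different (at least one known event of that grade), and the gap is visible in the missing row. Using the worst non-missing grade would turn Grade 1 plus missing into an apparently firm Grade 1. The reply adds that the SAP plans for all TEAEs to be graded, so the effect may be nil.

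Part of this stands. A worst non-missing grade is a lower bound, and for Grade 1 plus missing that should be made visible. The frequency is unknown and may be zero.

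The rest does not rescue the rule. No grade exceeds 5, so uncertainty cannot justify removing a known Grade 5. For Grade 4 plus missing, the subject is known to be at least Grade 4, and the missing category discards that. The Grade 1 plus missing subject is outside the Grade 3–5 columns under either rule, so the change never lowers a Grade 3–5 count. The missing row also does not explain the gap, because it mixes subjects who have a known Grade 3–5 event with subjects who do not.

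**Conclusion.** The concern holds. As written, the exception gives a wrong tabulation whenever a subject has both a known Grade 3–5 event and an ungraded event in the same SOC or PT, and that row then fails to reconcile with the Grade 3 or higher table.

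The likely size is small in PT rows and could be noticeable in busy SOC rows, on the assumed missing rates and event counts and with grades missing independently. The consequences are limited. The hidden events still appear in the Grade 3 or higher tables, in the serious and fatal TEAE tables where applicable, and in the listings. What is lost is the split among Grades 3, 4 and 5 in one descriptive table. No efficacy endpoint or DLT analysis is touched. It should be corrected because the error is avoidable and the correction costs almost nothing.

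**What to change.** In Section 7.5.2, replace the exception as it applies to severity with:

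> For the severity table, a subject is counted once at the worst non-missing grade within the SOC or PT, and as missing grade only if all grades within that SOC or PT are missing. Severity and relationship are handled separately.

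The last sentence also settles a second ambiguity: the present wording does not say whether a missing relationship alone sets the grade to missing. The relationship rule can stay as it is.

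Add a footnote giving the number of subjects with both known and missing grades, so that a worst grade which is only a lower bound remains visible.

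The cost is one sentence in the SAP, one footnote and a change of rank order in the by-grade table program. The table body no longer flags subjects with mixed known and missing grades; the footnote keeps that information.

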7.5.3 Clinical Laboratory Evaluation

Analysis set: SAF

All clinical laboratory evaluations including hematology and bone marrow, biochemistry, coagulation and urinalysis will be performed locally (for Phase 2 par, both centrally and locally).

The baseline visit is the last measurement taken prior to initial treatment.

Quantitative clinical laboratory variables, i.e. hematology, biochemistry, coagulation and urinalysis will be summarized using mean, standard deviation, minimum, maximum and median by measurement time point. Additionally, a within-subject change will be calculated as the post-baseline measurement minus the baseline measurement and summarized in the same way. Each laboratory result will be classified as L, N, or H by measurement time point according to supplied reference ranges. SI unit will be used for display. Summary shifts in each laboratory test result will be presented by measurement time point.

The number and percentage of subjects below and above reference range will be summarized by measurement time point.

Frequency tabulations of qualitative clinical laboratory variable (urinalysis) will be presented by measurement time point.

For hematology and biochemistry two types of shift tables will be presented:

- Shift tables of reference range changes from baseline to each treatment visit (low, normal, high), and
- Summary shifts of reference range changes from baseline to each treatment visit (shift from normal or high to low, shift from normal or low to high, categorized increase [shift from low to normal or from normal to high], categorized no change [value stays in the same reference range], categorized decrease [shift from high to normal or from normal to low]).

Laboratory results will also be graded using NCI-CTCAE, where possible. Parameters that have criteria available for both low and high values, i.e., hypo- and hyper-, will be summarized for both criteria. The same subject can be counted for both values if the subject has different laboratory values meeting each criterion. NCI-CTCAE grade of laboratory evaluations will be summarized by number and percentage of subjects by measurement time point. Shift tables of NCI-CTCAE grade change from baseline to worst post-baseline grade will also be presented.

Bone marrow results will be listed only.

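### In the laboratory summary shift table, a low-to-high shift is not counted as an increase and a high-to-low shift is not counted as a decrease, so the three direction classes cover 7 of 9 cells

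*SAP*

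**What the plan says.** Section 7.5.3 of the SAP sets the classification: "Each laboratory result will be classified as L, N, or H by measurement time point according to supplied reference ranges". It then plans two types of shift table for hematology and biochemistry.

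The first is the full cross-tabulation: "Shift tables of reference range changes from baseline to each treatment visit (low, normal, high), and".

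The second is a summary with five rows:

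- a row for ending low: "shift from normal or high to low";
- a row for ending high: "shift from normal or low to high";
- an increase row: "categorized increase [shift from low to normal or from normal to high"];
- a no-change row: "categorized no change [value stays in the same reference range"];
- a decrease row: "categorized decrease [shift from high to normal or from normal to low"].

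Section 7.1 adds a general rule: percentages by category use subjects with non-missing data as the denominator and are to total 100%.

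**The concern.** Increase, no change and decrease read as a complete three-way split of the direction of change. The bracketed definitions are closed lists with no indication that they are examples, and each names only single-step moves. The two moves that cross the whole reference range, which are the largest the classification can register, are therefore assigned to no direction class.

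The setting makes this more than a formality for hematology. Baseline is the last value before initial treatment, and the regimen includes induction chemotherapy, so a leukocyte count above range at baseline and below range at a later visit is a plausible pattern. A subject with that pattern would not be counted as having decreased. At stake are the counts in a planned safety table and whether its direction percentages can be read as a whole.

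**Working it through.** The plan gives no figure to reproduce here. The check is an enumeration.

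**Inputs.** There are three classes, L, N and H (section 7.5.3), so 3 × 3 = 9 baseline-to-visit cells. The row definitions are those quoted above. Write LH for the number of subjects low at baseline and high at the visit, and so on; n is the number with both values.

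**Assignment of each cell, as written.**

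| Cell | Ends-low row | Ends-high row | Direction class |
|---|---|---|---|
| LL | – | – | no change |
| LN | – | – | increase |
| LH | – | yes | none |
| NL | yes | – | decrease |
| NN | – | – | no change |
| NH | – | yes | increase |
| HL | yes | – | none |
| HN | – | – | decrease |
| HH | – | – | no change |

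**Coverage.** The direction classes hold 2 (increase) + 3 (no change) + 2 (decrease) = 7 of 9 cells. The missing two are LH and HL. All five rows together cover 9 of 9, because HL is in the ends-low row and LH in the ends-high row.

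**Sum of the direction classes.** (LN + NH) + (LL + NN + HH) + (HN + NL) = n − LH − HL. The percentages total 100% × [1 − (LH + HL)/n], which is below 100% whenever either cell is occupied.

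**Which rows the 100% rule can apply to.** The five rows together sum to n + NL + NH, since NL and NH each appear twice. The five are not one partition, so within this summary the rule in section 7.1 fits only the three direction classes, and those fail it.

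**Size of the understatement.** Increase is short by LH and decrease is short by HL, at each visit and for each parameter.

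**A visible symptom.** The ends-low row is NL + HL; the decrease row is HN + NL. If HL > HN, more subjects are shown as shifting down to low than are shown as decreasing at all.

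**After correction.** Increase = LN + NH + LH, no change = LL + NN + HH, decrease = HN + NL + HL. That is 3 + 3 + 3 = 9 cells, each covered once, summing to n. Decrease can then never be smaller than the ends-low row, nor increase smaller than the ends-high row.

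**The case against.** The strongest answer is that nothing is hidden. A high count that falls to low is in the ends-low row of the same summary, in the full low/normal/high shift table, and in the counts below reference range at each time point. Anyone interested in falls to low would use the row built for that purpose, and the correct direction counts can be rebuilt from the full table. This stands, and it sets the limit on the point. A reader might infer that the summary omits these shifts, or that affected subjects fall in no category; the documents do not support that, because the first two rows include both shifts explicitly.

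A reader might also infer that the rows contradict one another. They do not, simply by giving different counts: one pair of rows reports where the subject ended and the other three report direction, and overlap between them is by design. The defect is only that the direction set is incomplete.

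Finally, the brackets may be shorthand, and a programmer may assign low-to-high to increase without being told. Section 7.1 refers to separate table specifications that are not at hand and may settle this. That is possible, but the definitions as written are closed, and the same sentence names two-step shifts where it means to include them. The wording should not depend on a charitable reading.

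**Conclusion.** The defect is real but minor. As written, the increase, no-change and decrease classes cover 7 of 9 cells. They understate increases by the number of low-to-high subjects and decreases by the number of high-to-low subjects, and they fall short of 100% by the sum of the two shares. This rests on reading the bracketed definitions literally.

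The documents give neither the share of subjects out of range at baseline nor the share who cross the range, so any percentage of subjects affected would be an assumption, and none is offered. A reader might infer a large loss of safety information for leukocytes. That is not supported: the shifts remain reported elsewhere in the same section, and only the three direction classes are affected. No test, decision rule or efficacy conclusion depends on this table.

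**What to change.** In section 7.5.3, extend the increase definition to include a shift from low to high, and the decrease definition to include a shift from high to low. Leave the no-change class, the ends-low and ends-high rows, and the full shift table as they are. If the table specifications or the shift derivation already follow the literal brackets, align them with the new wording.

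The cost is one line of SAP text and a small change to the derivation. No further data are needed and no other analysis changes.

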7.5.3.1 Liver function tests

The following potentially clinically significant criteria in liver function tests for ALP, ALT, AST and their combination are defined. The subject's highest value during the investigational period will be used.

Parameter	Criteria
ALT	> 3xULN > 5xULN > 8xULN > 10xULN > 20xULN
AST	> 3xULN > 5xULN > 8xULN > 10xULN > 20xULN
ALT or AST	> 3xULN > 5xULN > 8xULN > 10xULN > 20xULN
Total Bilirubin	> 2xULN
ALP	> 1.5xULN
ALT and/or AST AND Total Bilirubin(*)	(ALT and/or AST > 3xULN) and total bilirubin > 2xULN
ALT and/or AST AND Alkaline Phosphatase AND Total Bilirubin(*)	ALT and/or AST > 3xULN AND Alkaline Phosphatase < 2xULN AND Total Bilirubin > 2xULN

(*) Combination of values measured within same sample

The number and percentage of subjects with potentially clinically significant values in liver enzymes and total bilirubin during the investigational period will be presented for Phase 1 part, Phase 2 part and Phase 1/Phase 2 part totally.

